In this study, 12 CD patients received osilodrostat orally for 10 weeks. The drug was given at the starting dose of 2 mg b.i.d., and was progressively increased on the basis of the urinary

cortisol levels till their normalization or a maximum dose of 50 mg b.i.d. was achieved. After 10 weeks of treatment, all 12 patients normalized urinary cortisol levels or achieved a > 50% reduction in urinary cortisol levels. The reduction of urinary cortisol levels was accompanied by a trend towards a decrease in BP. Osilodrostat was generally well tolerated, with the most frequently reported adverse events being fatigue (58.3%), nausea (41.7%), diarrhea (25%), headache (25%), hypokalemia (25%), muscle spasms (25%) and vomiting (25%).

Recently, an amended extension of the phase II study (CLCI699C2201, LINC 2) is currently ongoing with the overall objective of evaluating the efficacy and safety of osilodrostat for a longer period of time. After 22 weeks of treatment, 15 out of 19 patients (78.9%) had normalized UFC. The decrease in urinary cortisol levels was associated with improvements in the glucose and lipid profiles. Adverse events during this extension of the study included GI disturbances (nausea and diarrhea in 31.6%), asthenia (31.6%) and adrenal insufficiency (31.6%), together with an increase in ACTH, cortisol and aldosterone precursors, and an increase in testosterone, which, in some women was associated with onset or worsening of acne and hirsutism.

There was a trend toward improved fasting glucose and HbA1c in patients with diabetes at baseline, and an improved fasting lipid profile in patients with dyslipidemia at baseline.

After the initial 22 weeks (core study), patients were invited to enter the extension study up to month 31. Safety and efficacy results have shown that the drug's profile will fulfill the unmet need in the medical management of endogenous hypercortisolism because:

- Normal UFC was maintained for >2.5 years in a majority of patients.
- None of the patients with normalization of cortisol experienced escape from response
- Clinical measures improved, particularly body weight and BMI
- Occurrences of the most commonly reported AEs decreased over time

Therefore, osilodrostat seems to be a promising drug for the treatment of CD, with a satisfactory safety and tolerability profile.

Risks of osilodrostat treatment in study population

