Known risks of treatment with LCI699 in patients with CS include: QT prolongation, hypocortisolism/adrenal insufficiency, AEs related to the accumulation of precursor molecules, including: increased or decreased blood pressure, hypokalemia or hyperkalemia, hyponatremia, weight gain, edema, and increase in the synthesis of sex steroids (primarily adrenal androgens in women) that may lead to menstrual changes and hirsutism in women and acne in either men or women. Skin rash has been observed. Corticotroph tumor progression, with or without compressive symptoms, is a potential risk.

Neutropenia has been observed in a small number of patients with CD receiving osilodrostat. Preliminary assessment suggests that these events might be associated with cortisol levels that are either below normal or have had a rapid and substantial decline from baseline. In the observed cases, neutropenia rapidly reverses either spontaneously (typically after dose decrease) or with discontinuation of osilodrostat.

In addition, the protocol provides specific guidance for safety follow-up for liver toxicity (increased transaminases, increased total bilirubin) and an algorithm for monitoring and management of QT prolongation.

Conclusion

The treatment of patients with CS still represents a challenge: the available treatments do not lead to biochemical control in quite a large number of patients and many of them lose biochemical control over time.

Therefore there is an unmet medical need to develop new drugs with improved safety, efficacy and a more patient-friendly profile.

Based on current safety and efficacy data of osilodrostat, the overall benefit-risk of trial participation is expected to be positive for all subjects to be enrolled in this study.

5 Population

The investigator or designee must ensure that only patients who meet all the following inclusion and none of the exclusion criteria are offered treatment in the study.

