Symptomatic hypocortisolism or adrenal insufficiency	If the investigator at any time suspects hypocortisolism or adrenal insufficiency, they can immediately interrupt study drug and initiate replacement with glucocorticoids. Upon recovery as assessed by the investigator, glucocorticoid therapy can be tapered as tolerated, and study drug can be re-started. The decision to restart study drug will be made by the investigator. The AE and associated treatments with changes to study drug need to be appropriately documented in the eCRF. Recovery is assessed clinically by the investigator. A general guideline is that glucocorticoid taper can begin when cortisol in the upper part of the normal range or > ULN*, and study drug can be re-started if the patient is clinically stable off glucocorticoid therapy for at least one week, and the cortisol is normal or > ULN.
Persistent asymptomatic hypocortisolism (cortisol < LLN) at the lowest dose of LCI699 (1 mg every other day)	The investigator can interrupt study drug and restart at the same dose as clinically indicated.
Glucocorticoid withdrawal syndrome	Reduce or withhold dose until improved
*Hypotension (mild, reversible)	Reduce or withhold dose until improved
*Hypertension	Reduce or withhold dose until improved; consider angiotensin-converting-enzyme (ACE) inhibitors if appropriate for treatment of hypertension, or spironolactone as a second line treatment, particularly if hypokalemia is present. ACE inhibitors and spironolactone should not be used in combination.
*Weight gain, edema	Reduce or withhold dose until improved; consider spironolactone for treatment of edema.
*Hypokalemia	Consider reducing or withholding dose until improved; replace potassium; consider spironolactone or eplerenone for prevention and treatment of hypokalemia
*Hyperkalemia	Consider reducing or withholding dose until improved; if on spironolactone or eplerenone, reduce or withhold; treat with kayexalate and other potassium lowering therapies as needed.

Toxicity	Suggested Actions
*Hirsutism (women only)	Reduce or withhold dose until improved; review testosterone level; consider spironolactone, cyproterone acetate or finasteride per local guidelines.
*Acne (women or men)	Reduce or withhold dose until improved; review testosterone level; consider spironolactone, cyproterone acetate or finasteride per local guidelines.

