#### 6.2.3 Subgroup of interest

Not Applicable

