## 7.4 SAFETY ANALYSIS

Safety analyses will be performed on the Safety Set. The assessment of safety will be based mainly on the frequency of AEs, AESI and SAEs.

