### 7.4.1 Adverse events (AEs)

Treatment emergent AEs are defined as those that started on or after the study medication, or those that started before study medication but worsened afterwards. AEs starting after 30 days after last dose of Osilodrostat treatment are not considered treatment emergent AEs.

Summary tables for adverse events (AEs) have to include only AEs that started or worsened during the on-treatment period, the treatment-emergent AEs. However, all safety data (including those from the post-treatment periods) will be listed and those collected during the post-treatment period are to be flagged.

The incidence of treatment-emergent adverse events (new or worsening from baseline) will be summarized by system organ class and/or preferred term, severity based on CTCAE grades (version 4.03 or higher), type of adverse event, relation to study treatment. The summary will include AEs regardless of study-drug relationship. The same analysis will be repeated for SAEs.

All treatment emergent AEs and SAEs will be listed. In this listing, the information on the relationship to study treatment will be included.

---

Study Code: CLCI699C2X01B

Adverse events will be coded using the Medical dictionary for regulatory activities (MedDRA) terminology using the latest available MedDRA version at the time of the analyses and the information of MedDRA version will be specified in the footnote of relevant outputs.

The following selection of AEs will be listed and summarized separately using Safety Set. AEs will be summarized for all grades and for grade 3 or 4 side-by-side.

- AEs
- SAEs
- AEs leading to study drug discontinuation
- AEs requiring dose adjustment or interruption
- AEs requiring additional therapy
- Adverse events of special interest (AESI)

For the legal requirements of ClinicalTrials.gov and EudraCT, two required tables on treatment-emergent adverse events which are not serious adverse events with an incidence greater than 2% and on treatment-emergent serious adverse events and SAE suspected to be related to study treatment will be provided by system organ class and preferred term on the Safety Set population.

If for a same patient, several consecutive AEs (irrespective of study treatment causality, seriousness and severity) occurred with the same SOC and PT:

- A single occurrence will be counted if there is  $\leq 1$  day gap between the end date of the preceding AE and the start date of the consecutive AE

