#### 7.4.2 Laboratory parameters

Laboratory data summaries will include all assessments available for the lab parameters collected no later than 30 days of safety follow-up whichever is later after the last study treatment administration date using data from all sources. All laboratory assessments will be listed and those collected later than 30 days after the last study treatment date will be flagged in the listings.

Grading of laboratory values will be assigned programmatically as per NCI Common Terminology Criteria for Adverse Events (CTCAE) version 4.03 or higher. The calculation of CTCAE grades will be based on the observed laboratory values only, clinical assessments will not be taken into account. CTCAE version 5.0 will be applied and an extract of the tests that can be graded is reported in attachment 8.3.

CTCAE Grade 0 will be assigned for all non-missing values not graded as 1 or higher. Grade 5 will not be used. For laboratory tests that are graded for both low and high values, summaries will be done separately and labeled by direction, e.g., sodium will be summarized as hyponatremia and hypernatremia.

---

Study Code: CLCI699C2X01B

For laboratory tests where grades are not defined by CTCAE, results will be categorized as low/normal/high based on laboratory normal ranges.

For laboratory tests where grades are defined by CTCAE:

- Summary table for AEs of grades 3 or 4
- Shift tables using CTCAE grades to compare baseline to the worst on-treatment value
- Worst post-baseline CTCAE grade (regardless of the baseline status). Each patient will be counted only once for the worst grade observed post-baseline

For laboratory tests where grades are not defined by CTCAE,

- Shift tables using the low/normal/high/ (low and high) classification to compare baseline to the worst on-treatment value

The following listings will be produced for the laboratory data (hematology, and biochemistry):

- Listing of all laboratory data with values flagged to show the corresponding CTC grades the classifications relative to the laboratory reference ranges
- Listing of notable laboratory abnormalities (i.e., CTC grade 3 or 4 laboratory toxicities).

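### Hirsutism and menstrual events, which the protocol names as risks in women, are to be reported as percentages of men and women combined, and testosterone shifts are not split by sex

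*SAP*

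**What the plan says.** **The risk.** Protocol 4.5 lists among the known risks an "increase in the synthesis of sex steroids (primarily adrenal androgens in women) that may lead to menstrual changes and hirsutism in women". It also reports, from the extension of the earlier phase II study, "an increase in testosterone, which, in some women was associated with onset or worsening of acne and hirsutism". Protocol Table 6-2 has a row headed "Hirsutism (women only") and, directly after it, one headed "Acne (women or men").

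**The adverse-event tables.** SAP 7.4 states: "Safety analyses will be performed on the Safety Set". SAP 7.4.1 repeats this for the individual tables, including those for adverse events of special interest (AESI): "The following selection of AEs will be listed and summarized separately using Safety Set". SAP 6.2.2 defines the Safety Set as all patients who took at least one dose in the roll-over study. Under "Subgroup of interest", SAP 6.2.3 says only that the item does not apply. Sex is used in the demographic summary and listing (SAP 4.2.2) and nowhere else in the planned analyses.

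**The AESI list.** In SAP attachment 8.1, hirsutism, acne, hypertrichosis, hyperandrogenism and raised testosterone share one precursor-accumulation group with hypertension, hypokalaemia and oedema. No menstrual term is on the list.

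**Testosterone.** Protocol 4.5 schedules it every 24 weeks. SAP section 7 does not name it, and attachment 8.3 has no grade for it. The rule in SAP 7.4.2 for ungraded tests therefore applies: "Shift tables using the low/normal/high/ (low and high) classification to compare baseline to the worst on-treatment value".

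**The concern.** A percentage describes risk only if its denominator is the group that can have the event. Taking the protocol's own description, men cannot contribute to the numerator for hirsutism or menstrual changes, yet every treated man is in the denominator. The printed figure is then a product of the rate in women and the sex mix of whoever rolled over. It cannot be compared directly with a rate in women from another study, or with one from a sample with a different sex mix.

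For testosterone the issue is related but weaker. Men and women can both shift to high, so the pooled proportion is a weighted average of two populations in which the protocol expects the drug to act differently.

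Frequency of adverse events is the primary endpoint, and SAP 2.3 says interim safety tables go into periodic safety reports requested by a regulator. Androgen excess in women is one of the named long-term risks that these tables should describe.

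**Working it through.** **Figures in the plan.** There are none to reproduce. Protocol 12.8 gives no sample-size calculation, SAP 7.1.2 tests no hypothesis, and neither document states an expected rate of hirsutism or the trial's sex ratio.

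**Inputs**
- Hirsutism and menstrual changes treated as women-only: Protocol Table 6-2 and 4.5.
- Men are eligible: Protocol 5.1 and 5.2 set no sex restriction, and the acne row of Table 6-2 covers both sexes.
- Denominator is all treated patients: SAP 6.2.2, 7.4 and 7.4.1.
- Share of women, *f*: **assumed** 0.60 to 0.85. Protocol 1.1.1 says only that Cushing's disease affects markedly more women than men, and the trial admits every type of endogenous Cushing's syndrome.

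**Step 1: women-only events.** Let *p* be the rate in women.

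Printed rate = *f* × *p*. Relative shortfall = 1 − *f*.

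| Assumed *f* | Printed rate when *p* = 20% | Relative shortfall | Rate in women when 10% is printed |
|---|---|---|---|
| 0.60 | 0.60 × 20% = 12.0% | 40% | 10% / 0.60 = 16.7% |
| 0.75 | 0.75 × 20% = 15.0% | 25% | 10% / 0.75 = 13.3% |
| 0.85 | 0.85 × 20% = 17.0% | 15% | 10% / 0.85 = 11.8% |

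Widening *f* to 0.50–0.90 gives printed rates of 10.0% to 18.0% and shortfalls of 50% to 10%. The direction needs only one treated man and one event.

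**Step 2: testosterone shifting to high.** Let *r* be the rate in men divided by the rate in women.

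Pooled rate / rate in women = *f* + (1 − *f*) × *r*.

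| *f* | *r* = 0 | *r* = 0.5 | *r* = 1 | *r* = 1.5 |
|---|---|---|---|---|
| 0.60 | 0.60 | 0.80 | 1.00 | 1.20 |
| 0.75 | 0.75 | 0.875 | 1.00 | 1.125 |
| 0.85 | 0.85 | 0.925 | 1.00 | 1.075 |

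The pooled figure is too low for women when *r* < 1, correct when *r* = 1 and too high when *r* > 1. The documents give no value of *r*.

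**Step 3: what can be recovered.** Where hirsutism is tabulated, its count divided by the number of women in the demographic table gives the rate in women. A pooled shift table for testosterone does not show how many women are in each cell, so its split by sex cannot be recovered from the planned summaries.

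**Step 4: reporting thresholds.** The interim table by preferred term in SAP 2.3 requires at least 10% of all patients. Take 100 patients (enrolment at 8 April 2020, Protocol Amendment 02) and *f* = 0.75. Nine affected women are 9/100 = 9% of all patients and miss the table, but are 9/75 = 12% of women. For hirsutism this matters little, because the precursor-accumulation AESI table in the same list has no stated threshold. A menstrual term has no AESI table to fall back on.

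**The case against.** The strongest reply is that this is a matter of display. The endpoint is the frequency of adverse events in treated patients, and a Safety Set percentage answers that correctly. The study is descriptive and has no comparator, and the hirsutism rate in women is one division away. This is largely right for hirsutism, and it is why the point is an improvement and not an error in the estimate. It does not hold for testosterone, where the planned summaries do not contain the split.

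Several stronger readings are tempting, and the documents do not support them:

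- **A reader might infer that the testosterone rate in women is understated.** Step 2 shows that this depends on the rate in men. Protocol 4.5 places the androgen effect primarily in women, which suggests a lower rate in men but does not prove it.
- **A reader might infer that women's values are misclassified against men's limits.** SAP 7.4.2 refers to laboratory normal ranges without saying whether they are sex-specific. The parent-study data structure in attachment 8.2 carries limits on each laboratory record. If those limits are sex-specific, each patient's classification is sound and only the pooled display is affected.
- **A reader might infer that all androgen terms share the fault.** Acne is listed for both sexes, and nothing restricts hypertrichosis, alopecia, hyperandrogenism or raised testosterone to women. Their pooled denominator is valid.
- **A reader might infer that the printed figure reflects the sex mix and not the drug.** By the formula in Step 1 it reflects both.

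Two further cautions stand. Table 6-2 is guidance on dose modification, so its women-only label is a management label, though Protocol 4.5 describes the risk in the same way. And the unsplit testosterone table is inferred from a general rule, since SAP section 7 never names the test.

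**Conclusion.** The point holds in a limited form. For hirsutism and menstrual events the planned percentages fall below the rate in women by the fraction of the Safety Set who are men. At an assumed 60–85% women, that is a relative shortfall of 15–40%, so that a true 20% prints as 12–17%. The direction is certain once one man is treated and one event occurs. The size rests on a sex ratio that the documents do not give, and with a clear female majority it is moderate.

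For testosterone, the finding is that two populations are mixed in a table that cannot be separated afterwards. Neither the direction nor the size of the difference from the rate in women is established.

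No hypothesis test depends on this. It deserves a change because it concerns a named drug risk, the data are already collected, and the remedy is cheap.

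**What to change.** - **SAP 7.4.1:** report hirsutism and menstrual preferred terms with the number of treated women as denominator, beside the overall column. List the menstrual terms in advance, since attachment 8.1 has none. For these terms the denominator will still include post-menopausal women, which a footnote should say.
- **SAP 7.4.2:** name testosterone, show its shift table separately for women and men, and state that values are classified against sex-specific reference ranges.
- **SAP 6.2.3:** replace the current entry with a statement that these displays are by sex.
- **Optional:** show acne and the other androgen terms by sex.

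The cost is SAP wording and two small extra displays, with no new data. The cells for men will be small, so their percentages should be read with the counts.

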#### *Adverse events of special interest / grouping of AEs*

The specific categories of AEs of special interest list for LCI699 are listed in attachment 8.1.

#### 7.4.2 Laboratory parameters

Laboratory data summaries will include all assessments available for the lab parameters collected no later than 30 days of safety follow-up whichever is later after the last study treatment administration date using data from all sources. All laboratory assessments will be listed and those collected later than 30 days after the last study treatment date will be flagged in the listings.

Grading of laboratory values will be assigned programmatically as per NCI Common Terminology Criteria for Adverse Events (CTCAE) version 4.03 or higher. The calculation of CTCAE grades will be based on the observed laboratory values only, clinical assessments will not be taken into account. CTCAE version 5.0 will be applied and an extract of the tests that can be graded is reported in attachment 8.3.

CTCAE Grade 0 will be assigned for all non-missing values not graded as 1 or higher. Grade 5 will not be used. For laboratory tests that are graded for both low and high values, summaries will be done separately and labeled by direction, e.g., sodium will be summarized as hyponatremia and hypernatremia.

---

Study Code: CLCI699C2X01B

For laboratory tests where grades are not defined by CTCAE, results will be categorized as low/normal/high based on laboratory normal ranges.

For laboratory tests where grades are defined by CTCAE:

- Summary table for AEs of grades 3 or 4
- Shift tables using CTCAE grades to compare baseline to the worst on-treatment value
- Worst post-baseline CTCAE grade (regardless of the baseline status). Each patient will be counted only once for the worst grade observed post-baseline

For laboratory tests where grades are not defined by CTCAE,

- Shift tables using the low/normal/high/ (low and high) classification to compare baseline to the worst on-treatment value

The following listings will be produced for the laboratory data (hematology, and biochemistry):

- Listing of all laboratory data with values flagged to show the corresponding CTC grades the classifications relative to the laboratory reference ranges
- Listing of notable laboratory abnormalities (i.e., CTC grade 3 or 4 laboratory toxicities).

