1.2.1.2.1 Results of study LCI699C2201

Results of LCI699C2201 study in CD.

The purpose of the LCI699C2201 study was to determine whether the ability of osilodrostat to inhibit 11 β -hydroxylase could safely reduce UFC (Urinary Free Cortisol) in patients with CD.

This was initially studied over a 10-week treatment duration Proof-of Concept (Part I). Part II of the study aimed to further evaluate the observations from the Part I by enrolling a cohort of patients who participated in Part I and a new cohort (Expansion cohort) of patients and evaluating the long-term efficacy and safety of osilodrostat treatment.

In Part I, osilodrostat was effective in controlling cortisol production in all 12 patients studied. At daily osilodrostat doses between 2 mg twice a day (b.i.d.) and 50 mg b.i.d., 24-hour cortisol decreased rapidly and normalized at least once in all patients studied. In general at 5 mg b.i.d.

patients showed cortisol reduction after 2 weeks (at first cortisol measurement after dose titration).

The primary endpoint, defined as cortisol \leq Upper Limit Normal (ULN) or $\geq 50\%$ decrease from baseline at Day 70, was achieved by all patients. Overall, the mean time to response (UFC normalization or $\geq 50\%$ reduction from baseline) was 34.3 ± 14.1 days. The mean daily dose [\pm Standard Deviation (SD)] of osilodrostat required to reach the primary endpoint was 13.5 ± 13.9 mg b.i.d. with 75% of patients normalizing cortisol on ≤ 10 mg b.i.d. At Day 84, two weeks after osilodrostat was withdrawn, cortisol levels increased to a mean of 4-fold above upper limit of normal (ULN).

Significant decreases in mean plasma cortisol and aldosterone from baseline (-60% and -70%, respectively) and marked increases in their precursors from baseline (11-deoxycortisol [13-fold] and 11-deoxycorticosterone [42-fold], respectively) and ACTH [2.4-fold] were observed at Day 70. These biochemical changes were as expected based on the mechanism of action of the drug, i.e., primarily related to hypocortisolism, hypoaldosteronism, accumulation of their precursors, and increase in ACTH from baseline.

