4.2 Rationale for dose/regimen and duration of treatment

At the time of transition to this roll-over study, the starting dose should be the same as the last dose that was given at the last visit in the parent study. During the roll-over study, dose modification may be done at the discretion of the Investigator following the guidelines in [Section 6.5](#).

The maximum dose may not exceed 30 mg bid, which is the same maximum dose also applied in the parent studies.

Osilodrostat (LCI699) will be given in form of film-coated tablets for oral administration, and available in the following dose strengths: 1 mg, 5 mg and 10 mg.

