8.4.3 Laboratory evaluations

All laboratory evaluations will be performed using central laboratory according to the Assessment schedule: blood chemistry (Albumin, alkaline phosphatase, total bilirubin, calcium, creatinine, CK, GGT, inorganic phosphorus, lipase, amylase, magnesium, potassium, total protein, AST, ALT, sodium, urea/BUN and uric acid, HbA1c), hematology (Hemoglobin, hematocrit, red blood cell count, white blood cell count with differential, (monocytes, eosinophils, basophils, neutrophils, lymphocytes), and platelet count), testosterone, serum cortisol as clinically indicated, urine free cortisol (two 24-hour urine specimens collected), plasma ACTH, 11-deoxycortisol and 11 deoxycorticosterone.

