#### 4.1.1 General definitions

*Baseline*

---

Study Code: CLCI699C2X01B

For this study the baseline visit (W1D1) corresponds to the End of Treatment visit in the relative parent study.

The data for all assessments (except Obtain informed consent, Confirmation of Clinical Benefit from Study Treatment, and End of phase disposition) will be taken from the parent study.

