### 5 VARIABLES AND ENDPOINTS

Objectives and related endpoints are described in [Table 5-1](#) below altogether with the planned analysis of collected data.

Study Code: CLCI699C2X01B

Table 5-1 Objectives and related endpoints

Objective	Endpoint	Analysis
Primary		
To evaluate long term safety data, i.e., SAEs and AEs	Frequency and severity of AEs/SAEs	The assessment of safety will be based on the frequency and severity of adverse events (AEs) and serious adverse events (SAEs)
Secondary		
To evaluate clinical benefit as assessed by the investigator	Proportion of patients with clinical benefit as assessed by the investigator at scheduled visits	Proportion of patients with clinical benefit as assessed by the investigator will be summarized at scheduled visits
Other secondary		
To evaluate other safety data and tumor size	Lab parameters, vital signs, ECG, Tumor size and longest dimension	Shift tables vs Baseline and proportions of patients with notable abnormalities or grade 3 or 4

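### Hormones are tabulated only as low/normal/high shifts from an on-drug baseline to the worst value, which hides further change in patients already above ULN and hides UFC by visit.

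*SAP*

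**What the plan says.** Protocol 8.4.3 counts the hormones among the laboratory evaluations: "testosterone, serum cortisol as clinically indicated, urine free cortisol (two 24-hour urine specimens collected), plasma ACTH, 11-deoxycortisol and 11 deoxycorticosterone". Protocol 12.5.1.3 leaves the detail of the laboratory analysis to the SAP.

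SAP 7.4.2 has two routes. For graded tests, "CTCAE version 5.0 will be applied and an extract of the tests that can be graded is reported in attachment 8.3". For the rest, "For laboratory tests where grades are not defined by CTCAE, results will be categorized as low/normal/high based on laboratory normal ranges", and the one tabulation given for them is "Shift tables using the low/normal/high/ (low and high) classification to compare baseline to the worst on-treatment value". Attachment 8.3 has no entry for UFC, ACTH, 11-deoxycortisol, 11-deoxycorticosterone or testosterone, so all five take the second route. SAP Table 5-1 describes the same scope for the other secondary safety data: "Shift tables vs Baseline and proportions of patients with notable abnormalities or grade 3 or 4".

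On baseline, SAP 4.1.1 says: "For this study the baseline visit (W1D1) corresponds to the End of Treatment visit in the relative parent study". Patients carry their dose across; Protocol 4.2 says that "the starting dose should be the same as the last dose that was given at the last visit in the parent study". W1D1 is therefore an on-drug value.

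Elsewhere the SAP does plan change over time: for vital signs (7.4.3) and for tumour volume (7.4.5). It plans none for laboratory tests.

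**The concern.** Protocol 4.5 names adverse effects of precursor accumulation as a known risk of osilodrostat and corticotroph tumour progression as a potential one. The study exists to follow long-term safety, and it samples UFC and ACTH every 12 weeks and the precursors and testosterone every 24 weeks. A three-category scale has no resolution above ULN. If a patient is above ULN when the roll-over starts, the planned table cannot tell further accumulation from stability.

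UFC has a different weakness. Many repeated values are reduced to one worst value, so the table mixes how often UFC is out of range with how many visits the patient has had. Repeated hormone measurements would be collected without any planned summary of their course.

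**Working it through.** The documents give no sample size, power or hypothesis for this analysis, so there is no planned figure to reproduce. The check traces the rule and then illustrates its effect.

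**1. Precursors and ACTH: is a high baseline plausible?** Protocol 1.2.1.2.1 reports, at Day 70 of Part I of study C2201, "marked increases in their precursors from baseline (11-deoxycortisol [13-fold] and 11-deoxycorticosterone [42-fold], respectively) and ACTH [2.4-fold". These are means in 12 patients on doses up to 50 mg b.i.d. At a given fold-rise, a value exceeds ULN if the pre-drug value was above ULN divided by that rise:

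- 11-deoxycortisol: 1/13 = 7.7% of ULN
- 11-deoxycorticosterone: 1/42 = 2.4% of ULN
- ACTH: 1/2.4 = 41.7% of ULN

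A high value at W1D1 is therefore plausible, most clearly for the precursors, if rises of this order persist to the end of the parent study. This does not give the share of patients who are high. No fold-rise is quoted for testosterone.

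**2. What the shift rule does to a patient who starts high.** Assume W1D1 = 2 x ULN, 24-weekly samples, linear paths over 5 years and worst = highest. The tenth sample falls at 10 x 24/52.18 = 4.6 years.

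| Path | Last value (x ULN) | Worst value (x ULN) | Cell |
|---|---|---|---|
| Stable | 2.0 | 2.0 | high to high |
| Rise towards 10 | 2(1 + 4 x 4.6/5) = 9.36 | 9.36 | high to high |
| Fall towards 1.2 | 2 - 0.8 x 4.6/5 = 1.26 | 1.93 (first sample) | high to high |

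The cell changes only if the on-treatment values normalise or go low. A patient normal at W1D1 who rises above ULN still appears as normal to high.

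**3. UFC.** Three years at 12-week spacing gives 156/12 = 13 visits. Let q be the share of visits in range (an assumption; the documents give none for this study). The share of patients ever out of range is 1 - q under full within-patient correlation and 1 - q^13 if visits are independent.

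| q | Full correlation | Independent visits |
|---|---|---|
| 95% | 5% | 1 - 0.95^13 = 48.7% |
| 90% | 10% | 1 - 0.90^13 = 74.6% |
| 80% | 20% | 1 - 0.80^13 = 94.5% |

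The same per-visit control gives very different tables, so the table does not identify the control rate at any visit.

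**4. Off-drug samples.** Protocol 12.5.1.1 runs the on-treatment period to 30 days after the last dose, and SAP 7.4.2 includes laboratory values up to that limit. Protocol Table 8-1 schedules UFC at the 30-day follow-up. Protocol 1.2.1.2.1 reports mean cortisol at 4-fold above ULN two weeks after withdrawal. A follow-up UFC within the window can therefore become the worst on-treatment value although the patient is off drug.

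**The case against.** The study is descriptive, and the Protocol summary itself bases laboratory safety on values outside pre-determined ranges, so a range-based table is consistent with the protocol. Clinical consequences of accumulation are analysed elsewhere: blood pressure and weight over time (SAP 7.4.3), graded potassium and sodium (attachment 8.3), tumour volume change (7.4.5), and AESI terms that include raised precursors and testosterone (attachment 8.1). This cover is real but partial. Under Protocol 10.1.1 an abnormal value becomes an AE only if it causes signs or symptoms, is judged clinically significant or needs therapy, so the AESI tables do not follow hormone levels.

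A reader might also infer more than the documents support:

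- **That the table can show no accumulation at all, or that most patients start high.** Normal-to-high shifts remain visible. The fold-rises are means from 12 Cushing's disease patients on up to 50 mg b.i.d.; this study caps the dose at 30 mg b.i.d. and admits any endogenous Cushing's syndrome. The share above ULN at W1D1 is not given.
- **That nearly every patient would eventually read as out of range on UFC.** That needs independent visits and full five-year follow-up. Dose is adjusted to cortisol (Protocol 6.5.1.1), so within-patient correlation is expected. The five years run from first patient first visit; enrolment stood at 23 in January 2019 and 100 in April 2020, and patients leave when the drug is commercially available.
- **That an analysis of cortisol control has been left out.** Protocol 8.3.2 limits efficacy to clinical benefit. UFC belongs here as laboratory safety data.
- **That ACTH rises went with tumour enlargement on drug.** Protocol 1.2.1.2.2 says only that the two patients concerned had elevated ACTH, and the investigators suspected no relationship between the events and the drug.
- **That hormones will not be listed.** SAP 7.4.2 commits to listing every laboratory assessment; only its later bullet list is limited to hematology and biochemistry. That is an ambiguity, not an omission, and a listing does not summarise a trend.

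**Conclusion.** The point holds as a gap in the laboratory safety summaries. For a patient above ULN at W1D1, the planned table cannot show further accumulation or partial decline of ACTH, a precursor or testosterone. How many patients this affects is unknown; a high baseline is plausible for the precursors and ACTH and undocumented for testosterone. For UFC, the table shows whether a patient ever left the range, not control by visit: at an assumed 90% of visits in range over 13 visits, the share ever out lies between 10% and 75% depending on within-patient correlation, and off-drug follow-up samples may add to it. The AE-based primary analysis is not affected. The change should be made because the data are collected for this purpose and the better summary is cheap.

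**What to change.** In SAP 7.4.2 keep the existing shift tables and add, for ACTH, 11-deoxycortisol, 11-deoxycorticosterone, testosterone (by sex) and mUFC:

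1. By-visit n, median, quartiles and ratio to W1D1, with values also as multiples of ULN.
2. A shift table in multiples of ULN (for example up to 1, above 1 to 5, above 5 to 10, above 10), once with the last and once with the maximum on-treatment value.
3. By-visit percentages of mUFC below, within and above range, labelled as laboratory safety description and not as an efficacy endpoint.

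Show samples taken after the last dose separately. State that the commitment to list all laboratory assessments includes hormones. Reconcile the 24-weekly precursor sampling in Protocol 4.5 with Table 8-1, whose column from Week 60 onwards carries no mark for it, before fixing the by-visit shells.

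The cost is SAP wording and a few descriptive tables, with no new assessments; SAP 5.3 already plans the transfer of W1D1 laboratory data. Two limits should be stated with the tables. Ratios to W1D1 describe change during the roll-over only, not since before treatment. By-visit figures describe only patients still in the study, and those no longer benefiting leave, so n must appear at each visit with a note on selective exit.
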